4.1.5. Dose-Limiting Toxicity (DLT) Definition

The DLT window of observation for the purposes of dose escalation will be Cycle 1 defined as a subject receiving 3 doses of E-602 for monotherapy cohorts and 3 doses of E-602 and 1 dose of cemiplimab for combination therapy cohorts. Any of the following events will meet the definition

of a DLT if assessed by the investigator to be possibly, probably, or definitely related to study treatment:

- Any death not clearly due to the underlying disease or extraneous causes
- Hy's law:
 - o Aspartate aminotransferase (AST) or alanine aminotransferase (ALT) >3×the upper limit of normal (ULN) AND
 - o Total bilirubin >2×ULN AND
 - o Alkaline phosphatase <2×ULN AND
 - No other reason for liver injury
- Neutropenic fever
- Any Grade \geq 3 non-hematologic toxicity (with exceptions noted below)
- Grade 4 neutropenia or thrombocytopenia >7 days
- Grade 3 thrombocytopenia with bleeding
- Grade 4 vomiting or diarrhea of any duration
- Grade 3 fatigue ≥7 days
- Grade ≥3 electrolyte abnormality that lasts >72 hours, unless the subject has clinical symptoms, in which case all Grade ≥3 electrolyte abnormality regardless of duration will be a DLT.
- For subjects with hepatic metastases, AST or ALT >8×ULN or AST or ALT >5×ULN for ≥14 days
- Recurrent Grade 3 infusion-related reaction despite pre-medication
- Grade 4 infusion-related reaction on the first occurrence
- Dose delay of >14 days for the study treatment due to an AE

However, the following AEs are NOT considered a DLT:

- Hematologic toxicity:
 - o Grade 3 anemia
 - o Grade 3 lymphopenia
 - Grade 3 or 4 neutropenia that is not associated with clinical sequelae and lasts <7 days
 - o Grade 3 or 4 thrombocytopenia without bleeding
- Cardiovascular toxicity:
 - o Grade 3 hypertension
- Other toxicities:
 - o Grade 3 fatigue lasting <7 days
 - o Grade 3 nausea/vomiting or diarrhea for less than 72 hours with adequate antiemetic and other supportive care
 - Grade 3 or higher electrolyte abnormality that lasts up to 72 hours, is not clinically complicated and resolves spontaneously or responds to conventional medical interventions
 - Grade 3 or higher amylase or lipase that is not associated with symptoms or clinical manifestations of pancreatitis

- Isolated Grade 3 infusion reaction
- AEs that are clearly and incontrovertibly due to disease progression or extraneous causes.

Subjects treated in the Phase 1 dose escalation part of the study will discontinue treatment if he/she experience DLT(s) during Cycle 1.

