6.5. Dose Modification

To mitigate treatment-related toxicities, the following dosing modifications will be made for both E-602 monotherapy and for E-602 in combination with cemiplimab. When E-602 is used in combination, cemiplimab should be administered first and E-602 administered at least 30 minutes after the cemiplimab infusion is completed. Dose modifications for combination therapy apply to both E-602 and cemiplimab, and both study treatments must be held or restarted according to recommended dose modifications in Table 2. Dosing visits should not be skipped due to dose delays.

All therapies should be permanently discontinued if the study treatment is not restarted within 12 weeks after the last dose for the following:

- treatment-related toxicity, per Dose Modification (Table 2), does not resolve to Grade 0–1
- corticosteroid dosing cannot be reduced to ≤10 mg prednisone or equivalent per day
- any non-treatment related toxicity does not permit restarting study treatment

Table 2 Dose modifications for E-602 monotherapy and combination therapy with cemiplimab

Adverse Reaction	Severity (CTCAE v5.0)	Dose Modification/ Action with study treatment
Hematologic events	Any Grade 3 except thrombocytopenia with bleeding as specified below	Withhold until adverse reaction recovers to Grade 0–1
	Grade 4 neutropenia not associated with clinical sequelae	
	Grade 4 thrombocytopenia without bleeding	
	Grade 3 thrombocytopenia with bleeding	Permanently discontinue
	Any Grade 4 unless specified above or recurrent Grade 3	
	Neutropenic fever	

≥1 week

Protocol Number: PAL-E602-001

Version 8.0, 24 August 2023

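### Related Grade 4 thrombocytopenia without bleeding lasting more than 7 days in Cycle 1 falls on both the DLT list and the not-a-DLT list, and no rule says which list governs

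*Protocol*

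**What the plan says.** Protocol 4.1.5 gives two lists, and the synopsis repeats them. Events on the first list are DLTs if the investigator judges them possibly, probably or definitely related. That list includes "Grade 4 neutropenia or thrombocytopenia >7 days", "Grade 3 thrombocytopenia with bleeding" and "Dose delay of >14 days for the study treatment due to an AE". The second list, introduced by *However*, names events that are not DLTs. It includes "Grade 3 or 4 thrombocytopenia without bleeding" and "Grade 3 or 4 neutropenia that is not associated with clinical sequelae and lasts <7 days". The only explicit pointer from the first list to the exceptions is attached to the non-hematologic bullet.

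A subject in dose escalation "will discontinue treatment if he/she experience DLT(s) during Cycle 1". In Protocol 6.5, Table 2, "Grade 4 thrombocytopenia without bleeding" sits among the hematologic events for which treatment is withheld until recovery to Grade 0–1. "Any Grade 4 unless specified above or recurrent Grade 3" is among those requiring permanent discontinuation.

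Protocol 4.1.4 sets the cohort rules. At least 3 subjects must be DLT-evaluable. No DLT means escalate, 1 DLT in 6 evaluable means escalate, and 2 or more means the MTD is exceeded. Protocol 9.1 and SAP 3.2 count a subject without a DLT as evaluable only after all 3 E-602 doses (plus 1 cemiplimab dose in combination cohorts). SAP 4.3 takes its DLT definition from Protocol 4.1.5 and adds no rule.

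**The concern.** The same event can be classified two ways from the text as it stands. DLT incidence and the MTD are Phase 1 primary endpoints, so the classification can decide whether a cohort escalates, expands to 6 or stops. It also decides whether the subject has treatment withheld or discontinued. With no stated precedence, the choice would be made after the event is seen, in an open-label study, by a committee of principal investigators and Sponsor members.

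There is also a gap beside the overlap. No platelet bullet in the DLT list names Grade 4 thrombocytopenia with bleeding for 7 days or less, although Grade 3 with bleeding is a DLT at any duration.

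**Working it through.** **Plan's own figure.** The cohort rule reproduces the stated Phase 1 escalation maximum: 5 × 6 + 2 × 6 = 30 + 12 = 42. That figure is not in dispute.

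**Step 1: where the lists overlap.** The DLT entry requires Grade 4 and more than 7 days, with or without bleeding. The exclusion requires Grade 3 or 4 and no bleeding, for any duration. The overlap is Grade 4, no bleeding, more than 7 days. The parallel neutropenia entries do not overlap, because that exclusion stops short of 7 days.

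**Step 2: how narrow the case is.** I count days from the last dose given and assume that a delay runs from the due date of the missed dose. The next dose is due at day +7, so a delay exceeds 14 days after day +21. Cycle 1 hematology is scheduled on Days 1, 8 and 15. An event first seen at the day +7 draw and lasting 8 days is still Grade 4 until day +15. That leaves at most 21 − 15 = 6 days to recover to Grade 0–1. If recovery takes longer, the delay bullet makes the event a DLT under either reading. An event that begins after the Day 15 dose can also be disputed, and that subject already has the 3 doses needed for evaluability.

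**Step 3: evaluability.** If the event is a DLT, the subject is evaluable at once. If it is not, the subject is evaluable only after all 3 E-602 doses. Until then the outcome is to wait or replace, and with 3 treated subjects only 2 may be evaluable, which bars escalation.

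**Step 4: decisions when the subject is evaluable under both readings.** Filling to 6 is implied by the 1-in-6 rule.

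| Evaluable | Other DLTs | Disputed events | Not a DLT | DLT |
|---|---|---|---|---|
| 3–5 | 0 | 1 | escalate | fill to 6 |
| 3–5 | 1 | 1 | fill to 6 | MTD exceeded |
| 6 | 0 | 1 | escalate | escalate |
| 6 | 1 | 1 | escalate | MTD exceeded |
| 3–6 | 0 | 2 | escalate | MTD exceeded |
| 3–6 | 2 or more | any | MTD exceeded | MTD exceeded |

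**Step 5: size.** The documents give no event rates, so every rate here is assumed. Take 3 subjects, then 3 more if there is one DLT, all evaluable and independent, with total DLT rate p. Then P(escalate) = (1−p)³ + 3p(1−p)⁵. With other DLTs at 10%:

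- Not counted, p = 0.10: 0.7290 + 0.1771 = 0.906.
- Counted, event rate 0.1% (p = 0.101): 0.904.
- Counted, event rate 0.5% (p = 0.105): 0.898.
- Counted, event rate 1% (p = 0.110): 0.7050 + 0.1843 = 0.889.
- Counted, event rate 5% (p = 0.150): 0.814.

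At a 1% event rate the loss is 1.1, 1.7 or 2.2 percentage points for other-DLT rates of 5%, 10% or 20%. The chance of seeing at least one such event at that rate is 1 − 0.99³ = 3.0% in 3 subjects and 1 − 0.99⁶ = 5.9% in 6.

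Now suppose exactly one disputed event occurs among the first 3, that subject still completes all 3 doses, and no second disputed event follows. P(escalate) is (1−p)² + 2p(1−p)⁴ if it is not a DLT and (1−p)⁵ if it is, where p is now the other-DLT rate. At p = 0.10 these are 0.941 and 0.590.

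**The case against.** The strongest reply is that the text already has a natural order. A general list followed by *However* and a list of exclusions reads as a carve-out, and Table 2 agrees by withholding treatment for this event rather than stopping it. The event also appears unlikely. The monkey study found only minimal liver-enzyme changes, the clinical signal described in Protocol 2.3 is infusion reactions, and neither document mentions thrombocytopenia as an observed event. The safety committee reviews each cohort, and the RP2D rests on the totality of data and may be set before an MTD is reached.

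The points on rarity and oversight stand, and they set the severity. The carve-out reading is usable but is implied, not stated, and it leaves an odd remainder. The thrombocytopenia half of the >7 days bullet would then cover only Grade 4 with bleeding beyond 7 days, while Grade 3 with bleeding counts at any duration. The worse event would face the harder test. The neutropenia, fatigue and electrolyte exclusions all carry time limits, which suggests that one was left out here. The text supports either intention.

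A reader might infer from the bleeding gap that a subject with Grade 4 thrombocytopenia and bleeding could stay on treatment. Table 2 does not allow that, so only the DLT count is affected.

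**Conclusion.** The overlap is real as written, and no text in either document resolves it. The severity is minor. It matters only for a related Cycle 1 event without a dose delay over 14 days, and it changes escalation only in the configurations tabulated. At an assumed event rate of 1% or less with 10% other DLTs, it moves the chance of escalation by at most 1.7 percentage points. At a rate of zero it moves nothing.

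Three stronger conclusions are tempting, and the documents do not support them:

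- **That the gap between 94.1% and 59.0% is the effect on the trial.** It applies only once such an event has occurred in a subject who still completes all 3 doses.
- **That a past dose decision is in doubt.** Neither document reports the event.
- **That cohorts up to 10 mg/kg are cleared because Protocol 4.3.1 reports no DLTs and no related serious events there.** Under the not-a-DLT reading a disputed event would also have been reported as no DLT, and a low count without symptoms need not be serious.

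**What to change.** In Protocol 4.1.5 and the synopsis, choose one:

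1. Restrict the exclusion to *Grade 3 thrombocytopenia without bleeding, or Grade 4 without bleeding lasting ≤7 days*.
2. If the exclusion is meant to override, delete thrombocytopenia from the >7 days bullet.

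In either case, change the bleeding bullet to *Grade ≥3 thrombocytopenia with bleeding*. Under option 1, add a cross-reference from the Table 2 withhold row to the Cycle 1 DLT discontinuation rule, unless one is already there (Table 2 is only partly legible in the text available). If the safety committee looks back for affected decisions, it should cover all completed cohorts.

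The cost is a wording edit in two places, plus one cross-reference under option 1. It needs IRB approval as an amendment, so it can travel with the next one. No new data or subjects are needed, and SAP 4.3 follows by reference.

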9.1. Analysis Sets

DLT Evaluable Set:

Will include all subjects treated in the dose escalation part who have had a DLT within Cycle 1 on study or without a DLT but completed safety assessments through Cycle 1 (3 doses of E-602 administered for monotherapy cohorts and 3 doses of E-602 and 1 dose of cemiplimab administered for combination therapy cohorts). The DLT Evaluable Set will be defined for each dose cohort. Subjects who discontinue prior to completing Cycle 1 (3 doses of E-602 administered for monotherapy cohorts and 3 doses of E-602 and 1 dose of cemiplimab administered for combination therapy cohorts) for reasons other than toxicity may be replaced.

Safety Analysis Set:

Will include all subjects who have received any dose of study treatment. The Safety Analysis Set will be used for safety analyses. Safety Analysis Set may be further defined by the phase of the study, dose, and tumor type.

Efficacy Evaluable Set:

Will include all subjects who receive any dose of study treatment, meet eligibility criteria, have measurable tumor lesions at baseline, and have at least one post-baseline disease assessment per RECIST v1.1. Efficacy Evaluable Set is defined for each cohort in the Phase 2 separately.

Pharmacokinetics (PK) Analysis Set:

Will include all subjects in the Safety Analysis Set for whom adequate data on E-602 plasma concentration are available.

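### Two Grade 4 blood events that end treatment (anemia, and short thrombocytopenia with a minor bleed) are neither DLTs nor exempt, so the 3+3 count can miss them

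*Protocol*

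**What the plan says.** **DLT list (Protocol 4.1.5, repeated in Synopsis 1.1).** An event counts only if it is listed and the investigator judges it at least possibly related. The general Grade ≥3 item is limited to non-hematologic toxicity. The hematologic items are neutropenic fever, "Grade 4 neutropenia or thrombocytopenia >7 days" and "Grade 3 thrombocytopenia with bleeding". A separate item is "Dose delay of >14 days for the study treatment due to an AE".

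**Exemptions (same section, introduced by However).** These include Grade 3 anemia, Grade 3 lymphopenia, "Grade 3 or 4 neutropenia that is not associated with clinical sequelae and lasts <7 days" and "Grade 3 or 4 thrombocytopenia without bleeding".

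**Dose modification (Protocol 6.5, Table 2).** Most Grade 3 hematologic events, Grade 4 neutropenia without sequelae and Grade 4 thrombocytopenia without bleeding carry the action "Withhold until adverse reaction recovers" to Grade 0–1. Permanent discontinuation applies to Grade 3 thrombocytopenia with bleeding, neutropenic fever and "Any Grade 4 unless specified above or recurrent Grade 3".

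**Who is counted (Protocol 9.1; SAP 3.2).** The DLT Evaluable Set takes escalation subjects "who have had a DLT within Cycle 1 on study or without a DLT but completed safety assessments through Cycle 1", with Cycle 1 defined by three E-602 doses (plus one cemiplimab dose in combination cohorts).

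**Count rule (Protocol 4.1.4).** A cohort first treats 3–6 subjects, and at least 3 must be evaluable. With 0 DLTs, or 1 in 6 evaluable, the dose goes up. With 2 or more, the MTD is exceeded.

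SAP 4.3 refers back to Protocol 4.1.5 and adds no event.

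**The concern.** Some hematologic events that the protocol treats as severe enough to end treatment have no DLT status. The bleeding item also runs in the wrong direction: read literally, Grade 3 thrombocytopenia with a minor bleed counts and Grade 4 with the same bleed does not, unless it lasts more than 7 days.

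The MTD is a primary Phase 1 endpoint based on DLT occurrence, and this is a first-in-human trial. If a treatment-ending related event is outside both the numerator and the evaluable set, the stated rule can send the next cohort to a higher dose on a count that looks clean. The selected dose then goes forward to as many as 186 Phase 2 subjects.

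**Working it through.** The plan states no figure here, so the check is of rule completeness, followed by what the count rule does with the gap.

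**Step 1. Classify related Cycle 1 events against 4.1.5 and Table 2.**

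| Event | DLT item? | Exempt? | Table 2 |
|---|---|---|---|
| Grade 3 thrombocytopenia, Grade 1–2 bleed | Yes | No | Discontinue |
| Grade 4 thrombocytopenia ≤7 days, Grade 1–2 bleed | **No** | **No** | Discontinue |
| Same, Grade ≥3 bleed | Yes (the bleed is non-hematologic) | No | Discontinue |
| Grade 4 thrombocytopenia >7 days, with bleed | Yes | No | Discontinue |
| Grade 4 anemia, any duration | **No** | **No** | Discontinue |
| Grade 4 neutropenia ≤7 days with sequelae, no neutropenic fever and no Grade ≥3 non-hematologic event | **No** | **No** | Discontinue |
| Grade 4 thrombocytopenia >7 days, no bleed | Yes | Yes | Withhold |

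Grade 4 lymphopenia is also on neither list. Whether it should count is a clinical choice, and this point does not rest on it.

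**Step 2. Place the stopped subject.** If stopped before dose 3, the subject has no DLT and has not completed Cycle 1, so is outside the DLT Evaluable Set. If stopped after dose 3 with Cycle 1 assessments complete, the subject can be an evaluable non-DLT.

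**Step 3. Apply the count rule.** Let n be the number treated and k the number stopped before dose 3 for an unlisted event, with the rest DLT-free. Evaluable = n − k.

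| n | k | As written | If the events counted |
|---|---|---|---|
| 3 | 1 | 2 evaluable, cannot escalate yet | 1 DLT |
| 4 | 1 | 0 of 3, escalate | 1 DLT, 6 evaluable needed |
| 5 | 2 | 0 of 3, escalate | 2 DLTs, MTD exceeded |
| 6 | 3 | 0 of 3, escalate | 3 DLTs, MTD exceeded |

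This step needs no assumed rate.

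**Step 4. Illustrate the size.** The documents give no event rates, so these are assumptions. Let d be the listed DLT probability and q the probability of an unlisted event before dose 3 in a subject without a listed DLT. Subjects are independent, are added one at a time, and at most 6 are treated. Put u = (1−d)q and e = (1−d)(1−q).

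- As written: P(escalate) = e³(1 + 3u + 6u² + 10u³) + 3d·e⁵
- If counted, with t = d + u: P(escalate) = (1−t)³ + 3t(1−t)⁵

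For d = 0.10 and q = 0.05, u = 0.045, e = 0.855 and t = 0.145. As written: 0.6250 × 1.1481 + 0.1371 = 0.855. Counted: 0.6250 + 0.1988 = 0.824. At q = 0 both give 0.906.

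| q (d = 0.10) | As written | Counted | Gap |
|---|---|---|---|
| 0.01 | 0.895 | 0.891 | 0.004 |
| 0.05 | 0.855 | 0.824 | 0.031 |
| 0.10 | 0.809 | 0.730 | 0.079 |
| 0.20 | 0.727 | 0.536 | 0.191 |

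Over the same q, the gap runs from 0.003 to 0.231 at d = 0.05 and from 0.005 to 0.125 at d = 0.20.

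**Step 5. Vary the model.** If an unlisted subject is always replaced without limit, or counts as an evaluable non-DLT, the as-written probability stays at 0.906. Adding 5, 10 or 20 percentage points to a 10% DLT rate gives 0.814, 0.709 or 0.494 when counted, so gaps of 0.092, 0.197 or 0.412. The size therefore depends on the model as well as the rate.

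**The case against.** **The replacement text points to a different intent.** Protocol 9.1 and SAP 3.2 allow replacement of subjects who leave Cycle 1 early for reasons other than toxicity, and Protocol 7.1.2 gives departures unrelated to treatment toxicity as its example. This suggests that toxicity dropouts were meant to count. It stands as evidence of intent, but no DLT item carries it out. Nor does it block Step 3, because 4.1.4 allows 3–6 subjects from the start.

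**Other items might catch these events.** Grade 3 with bleeding could be read to include Grade 4. But the same section writes Grade ≥3, or Grade 3 or 4, where it means both, and this reading does nothing for anemia. The delay item might be stretched to cover discontinuation, but Table 2 treats withholding and permanent discontinuation as separate actions.

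**Escalation is not mechanical.** The safety data review committee advises on every escalation decision, using accumulating data (Synopsis; SAP 7.1), SAEs are reported within 24 hours, and escalation also ends on unacceptable toxicity (Protocol 4.1.1). A committee would be unlikely to pass over 3 of 6 subjects stopped for related Grade 4 events. This mitigates the gap, but it is discretionary: none of these provisions sets a number or ties Table 2 discontinuations to the count.

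**The events may be rare.** Monkey toxicology showed only minimal liver-enzyme changes (2.2.1.3). No DLTs were reported up to 10 mg/kg, and no E-602-related SAEs, as of 23 September 2022 (4.3.1). Entry requires platelets of at least 100,000 cells/mm³ and hemoglobin of at least 9.0 g/dL. This stands, and it keeps the likely effect small.

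**A reader might infer that 4.1.5 contradicts itself** on Grade 4 thrombocytopenia beyond 7 days without bleeding, since it matches both a DLT item and an exemption. The documents do not support so strong a charge. The exemption list opens with However, which appears to give it precedence, and Table 2 withholds for that event with no duration limit. It is an overlap that needs a choice.

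**Conclusion.** The gap is real and should be fixed. Related Grade 4 anemia and Grade 4 thrombocytopenia of 7 days or less with a Grade 1–2 bleed have no DLT status, although Table 2 ends treatment for both and a lesser form of the second is a DLT. Grade 4 neutropenia with sequelae has the same gap in narrow circumstances.

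On a literal reading, the count rule can escalate on 0 DLTs with 1 of 4, 2 of 5 or 3 of 6 treated subjects permanently stopped. That rests only on the written definitions. The probabilities rest on assumed rates and independence: the gap is negligible near 1% and material only if such events are common, for which the documents give no evidence.

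A reader might infer that a dose was wrongly cleared or a subject harmed. Nothing in the documents shows that. This is an error in the rule, with discretionary safeguards around it.

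**What to change.** In Protocol 4.1.5 and the synopsis copy:

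1. Change the bleeding item to *Grade ≥3 thrombocytopenia with bleeding*.
2. Add *Grade 4 anemia* and *Grade 4 neutropenia with clinical sequelae, any duration* as DLTs. Both match Table 2's permanent-discontinuation row.
3. Re-check Cycle 1 hematologic events already observed against the revised list.

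Secondary: state which reading governs Grade 4 thrombocytopenia beyond 7 days without bleeding. If it is exempt, limit the >7-day thrombocytopenia item to cases with bleeding. If it is to be a DLT, narrow the exemption and also change the Table 2 withhold row, because 4.1.5 requires escalation subjects to stop treatment after a Cycle 1 DLT.

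SAP 4.3 follows automatically through its reference to 4.1.5. The cost is a wording amendment and one data review, with no new procedures. The downside is that a newly counted event could expand a cohort to 6 evaluable subjects, or slow or stop escalation.

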4.2. Scientific Rationale for Study Design

This study is a combination of a Phase 1, FIH, dose escalation study and a Phase 2, dose expansion study. Subjects to be treated in the study are those with advanced cancers, and a control group is not deemed appropriate.

In this study, the effects of desialylation of immune and tumor cells on the antitumor immunity will be explored, with E-602 given as a monotherapy and together with a PD1-pathway inhibitor. The tumor types chosen to be studied are populations enriched for patients with tumors that have greater amounts of sialoglycan modifications with immunoinhibitory potential, such as melanoma (Prendergast 2021), lung, colon, pancreatic, ovarian, breast, gastric/EGJ, head and neck and urothelial cancers (data on file).

In Phase 1 of the study, dose escalation (5 dose levels planned) will follow a modified 3+3 design for the E-602 monotherapy, and dose escalation (2 dose levels) for the combination therapy with cemiplimab will be carried out after the same dose level in monotherapy has been deemed tolerable. This design will assure protection of subject safety while identifying an MTD and an appropriate dose for dose expansion in Phase 2. Phase 1 cohorts can be backfilled at the judgement of the Sponsor in a dose cohort as needed to obtain additional safety, PK, and pharmacodynamic data at a particular dose level.

The RP2D(s) for monotherapy and combination therapy will be selected separately based on the totality of data including safety, pharmacodynamic, and PK data collected during Phase 1.

